### **3.7.3.3 Physical Examination and Vital Signs**

#### **3.7.3.3.1 Physical Examination**

The physical examination will consist of measurement of height and a review of the following body systems: head, ears, eyes, nose, and throat; thorax; abdomen; urogenital; extremities; neurological; and skin and mucosae. Height will be measured with a stadiometer, measuring stick or tape. The principal investigator or his/her appointed designee is primarily responsible to perform the physical examination. If the appointed designee is to perform the physical examination, he/she must be permitted by local regulations and his/her name must be included on the FDA Form 1572. Whenever possible, the same individual should perform all physical examinations. Any condition present at the post-treatment physical examination that was not present at the baseline examination should be documented as an AE and followed to a satisfactory conclusion.

A complete physical examination is an integral part of study safety assessments and includes a urogenital assessment. A urogenital assessment should be performed on all trial subjects according to local medical standards as applied to other body systems. For the purposes of this trial, at a minimum, a baseline urogenital exam is required which could have been performed up to 1 calendar year prior to the date of ICF being signed, or can be performed during the screening period. Additionally, at the Trial 331-10-236 rollover screen baseline visit, the information will have been collected as part of the Trial 331-10-234 Week 6 visit. The urogenital examination may be performed by the subject's primary care provider or pediatrician as long as the source records are obtained and the findings documented. Post-baseline, medically relevant questions about the urogenital body system must be asked of the subject at all protocol-required physical exams, with answers documented accordingly in the source. The extent and scope of any part of the physical examination is to be left to the discretion of the investigator as deemed appropriate for each subject.

The following procedures will aid in the standardization of waist circumference measurements:

- The subject should be minimally clothed (ie, lightweight clothing; no heavy overgarments).
- Waist circumference should be recorded before a subject's meal and at approximately the same time at each visit.

- Measurement will be accomplished by locating the upper hip bone and the top of the right iliac crest and placing a weighted measuring tape in a horizontal plane around the abdomen at the level of the crest. Before reading the tape measure, the assessor should assure that the tape is snug, but does not compress the skin, and is parallel to the floor. The measurement is to be made at the end of a normal exhalation.

### **3.7.3.3.2      Vital Signs**

Vital sign measurements will include body weight, body temperature, systolic blood pressure (SBP), diastolic blood pressure (DBP), and heart rate. The following guidelines will aid in the standardization of body weight measurements:

- The same scale should be used to weigh a given subject each time, if possible.
- Scales should be calibrated and reliable; scales should be at zero just prior to each subject's weigh-in session.
- A subject should void prior to being weighed and be minimally clothed (ie, no shoes or heavy overgarments).
- Weight should be recorded before a subject's meal and at approximately the same time at each visit.

Blood pressure and heart rate measurements will be made in the supine, sitting, and standing positions after the subject has been in each position for at least 3 minutes. The supine measurements will be performed first, followed by sitting, and finally standing. Vital signs scheduled at the same visit as blood samples are to be completed before blood is drawn.

Subjects should be excluded if they have any vital sign measurement at screening that, in the investigator's judgment, is medically significant in that it would impact the safety of the subject or the interpretation of the trial results. However, any abnormal screening vital sign result(s) considered to be clinically significant may be repeated once to confirm the finding(s) before excluding the subject from the trial. [Appendix 1](#) is included to assist investigators in their assessments of results that may be potentially medically significant, depending on the subject's medical history and clinical presentation.

### **3.7.3.4      *Electrocardiogram Assessments***

Twelve-lead ECG recordings will be obtained after the subject has been supine and at rest for at least 5 minutes. Additional 12-lead ECGs may be obtained per the investigator's discretion and should always be obtained in the event of an early termination. A central ECG service will be utilized for reading all ECGs in order to standardize interpretations for the safety analysis. In addition, ECG results will be evaluated at the investigational site to monitor safety during the trial. The principal investigator or qualified designee will review each ECG reading, noting whether or not any abnormal results are of clinical significance. The ECGs should be repeated 1 time if a result is considered to be clinically significant.

A screening ECG finding of QTcF or QTcN  $\geq 450$  msec for males and  $\geq 470$  msec for females based on the results from the central reader is exclusionary (see [Table 3.4.3.1-1](#) for rollover subjects and [Table 3.4.3.2-1](#) for de novo subjects). In addition, subjects should be excluded if they have any other abnormal ECG finding at screening that, in the investigator's judgment, is medically significant in that it would impact the safety of the subject or the interpretation of the trial results. However, any screening ECG with abnormal result(s) considered to be clinically significant should be repeated as soon as possible to confirm the finding(s) before excluding the subject from the trial. [Appendix 3](#) is provided as a guide for determining potentially clinically relevant ECG abnormalities. For both rollover subjects from Trial 331-10-234 and de novo subjects, central reader results for verification of exclusion criteria at baseline visit will not be available prior to dosing; therefore, subjects will be enrolled based on screening ECG results from the central reader and baseline ECG results from the trial site. However, if the baseline ECG results from the central reader, when available, indicate a QTcF or QTcN  $\geq 450$  msec for males and  $\geq 470$  msec for females at baseline, the investigator must contact the medical monitor to discuss the subject's continued participation in the trial.

### **3.7.3.5      *Other Safety Assessments***

It is required that a trained and experienced clinician administer the safety assessments, including the EPS scales (SAS, AIMS, and BARS), C-SSRS, UKU, NY-AACENT, and Tanner Staging Scale assessment. The number of raters within each trial site should be kept to a minimum. All efforts will be made to ensure that the same clinician administers the scales for a given subject. Notations in the subject's trial records should substantiate the ratings. Training and materials for rating will be provided by Otsuka or designee.

### **3.7.3.5.1      Simpson Angus Scale**

The SAS ([Appendix 9](#)) consists of a list of 10 symptoms of Parkinsonism (gait, arm dropping, shoulder shaking, elbow rigidity, wrist rigidity, head rotation, glabella tap, tremor, salivation, and akathisia). Each item will be rated on a 5-point scale, with a score of zero representing absence of symptoms, and a score of 4 representing a severe condition. The SAS Total Score is the sum of the scores for all 10 items.

Anticholinergics, propranolol, benzodiazepines, and non-benzodiazepine sleep aids are not permitted within 12 hours of scale administration (see [Section 4](#)). Investigators are encouraged to delay scale administration until 12 hours have elapsed, if at all possible. However, if delaying administration of the scale is not feasible, the SAS should still be administered and the use of the medication documented, including a notation of the drug name, dose, and time of administration on the eSource.

### **3.7.3.5.2      Abnormal Involuntary Movement Scale**

The AIMS assessment ([Appendix 10](#)) consists of 10 items describing symptoms of dyskinesia. Facial and oral movements (items 1 through 4), extremity movements (items 5 and 6), and trunk movements (item 7) will be observed unobtrusively while the subject is at rest (eg, in the waiting room), and the investigator will also make global judgments on the subject's dyskinesias (items 8 through 10). Each item will be rated on a 5-point scale, with a score of zero representing absence of symptoms (for item 10, no awareness), and a score of 4 indicating a severe condition (for item 10, awareness, severe distress). For this scale, the subject is to be sitting on a hard, firm chair. In addition, the AIMS includes two yes/no questions that address the subject's dental status. Anticholinergics, propranolol, benzodiazepines, and non-benzodiazepine sleep aids are not permitted within 12 hours of scale administration (see [Section 4](#)). Investigators are encouraged to delay scale administration until 12 hours have elapsed, if at all possible. However, if delaying administration of the scale is not feasible, the AIMS should still be administered and the use of the medication documented, including a notation of the drug name, dose, and time of administration on the eSource.

The AIMS Movement Rating Score is defined as the sum of items 1 through 7 (ie, items 1 through 4, facial and oral movements; items 5 and 6, extremity movements; and item 7, trunk movements).

### **3.7.3.5.3 Barnes Akathisia Rating Scale**

The BARS ([Appendix 11](#)) consists of 4 items related to akathisia: objective observation of akathisia by the investigator, subjective feelings of restlessness by the subject, subjective distress due to akathisia, and global clinical assessment of akathisia. The first 3 items will be rated on a 4-point scale, with a score of zero representing absence of symptoms and a score of 3 representing a severe condition. The global clinical evaluation will be made on a 6-point scale, with zero representing absence of symptoms and a score of 5 representing severe akathisia. To complete this scale, subjects will be observed while they are seated and then standing for a minimum of 2 minutes in each position. Symptoms observed in other situations (eg, while engaged in neutral conversation or engaged in activity on the ward) may also be rated. Subjective phenomena are to be elicited by direct questioning. Anticholinergics, propranolol, benzodiazepines, and non-benzodiazepine sleep aids are not permitted within 12 hours of scale administration (see [Section 4](#)). Investigators are encouraged to delay scale administration until 12 hours have elapsed, if at all possible. However, if delaying administration of the scale is not feasible, the BARS should still be administered and the use of the medication documented, including a notation of the drug name, dose, and time of administration on the eSource.

The BARS Global Score is defined as the global clinical assessment of akathisia.

### **3.7.3.5.4 Udvalg for Kliniske Undersogelser**

The UKU scale has been included in this trial to satisfy regulatory authorities. The UKU is used to assess side effects of subjects being treated with antipsychotic drugs and to determine whether there is a causal relationship. A copy of the UKU is provided in [Appendix 12](#).

### **3.7.3.5.5 New York Assessment for Adverse Cognitive Effects of Neuropsychiatric Treatment**

The NY-AACENT is not a validated scale. It has been included in this trial to satisfy regulatory authorities. No validated scale addressing these issues is currently available.

The NY-AACENT is used to detect changes in cognitive function subsequent to pharmacological or similar treatments for neurological or psychiatric problems. It is specifically designed to be used in pediatric populations (ages 12-17 years), but can be utilized with other age groups as appropriate. The clinician-administered NY-AACENT will be completed per the schedule of assessments ([Table 3.7-1](#) for rollover subjects and [Table 3.7-2](#) for de novo subjects).

The clinician form is attached in [Appendix 13](#).

### **3.7.3.5.6      Tanner Staging Scale**

The collection of Tanner Staging data is required for this trial, and every attempt should be made to collect this information. Tanner Staging must be completed together with the physical examination by the same trial-affiliated clinician in the most inconspicuous manner for the subject as possible. Tanner Staging could be completed by trial psychiatrist, trial-affiliated pediatrician or family practitioner (additionally physician's assistant or nurse-practitioner in the US). When Tanner Staging is not completed at a required visit, it should be performed at the next trial visit.

Tanner Staging will be recorded at the visits specified in [Table 3.7-1](#) for rollover subjects and [Table 3.7-2](#) for de novo subjects. The Tanner Staging Scale assessment consists of 2 domains (pubic hair and breast development) for girls and 3 domains (pubic hair, penis development, and testes development) for boys. The Tanner Staging Scale assessment as a reference for the completing clinician is included in [Appendix 14](#). A subject who reaches Stage 5 (both in pubic hair and genitalia) does not need to continue with Tanner Staging. The clinician will arrive at a single score summarizing the domains (not individual domain scores) when evaluating the subject.

Any psychiatrist who will perform the Tanner Staging Scale evaluation will be trained and required to demonstrate inter-rater reliability before receiving certification to conduct the evaluation. A family practitioner or pediatrician who are investigators are considered trained and do not need to go through formal inter-rater reliability. Sites should make attempts to have examiners of both gender types. Attempts should be made to have examination performed by the same gender as the subject. Otherwise, trial-affiliated personnel of the same gender as the subject (ie, nurse) should be in the same examination room as the subject.

### **3.7.3.5.7      Suicidality**

Suicidality will be monitored during the trial using the Columbia-Suicide Severity Rating Scale (C-SSRS). This trial will use the “Baseline/Screening” and “Since Last Visit” versions of the scale. The “Baseline/Screening” version, which assesses the lifetime experience of the subject with suicide events and suicidal ideation and the occurrence of suicide events or ideation within a specified time period prior to entry into the trial, will be completed for all de novo subjects at the screening visit to determine the eligibility (prior to the first dose of open-label brexpiprazole). Any subject with active suicidal ideation within the last 30 days, suicidal behaviors within the last year, or who in the

clinical judgment of the investigator presents a serious risk of suicide should be excluded from the trial (see [Table 3.4.3.1-1](#) for rollover subjects and [Table 3.4.3.2-1](#) for de novo subjects). The “Since Last Visit” C-SSRS form will be completed at all other in-clinic visits for all subjects (rollover and de novo). Copies of the C-SSRS forms are provided in [Appendix 15](#).

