### 3.4.3 Exclusion Criteria

#### 3.4.3.1 Rollover Subjects

Subjects will be excluded if they meet any of the exclusion criteria in [Table 3.4.3.1-1](#). Some laboratory results may not be available from the last visit at the time of entry into the open-label treatment period in this trial. Investigators will need to contact the medical monitor if there are any clinically significant laboratory results to discuss a subject's ability to continue in the trial.

| Table 3.4.3.1-1      Exclusion Criteria for Rollover Subjects from Trial 331-10-234 |   |
|--|---|
| Sex and Reproductive Status   |   |
| 1.   | Sexually active males or females who do not agree to practice 2 different methods of birth control or remain abstinent during the trial and for 30 days after the last dose of IMP. If employing birth control, 2 of the following precautions must be used: vasectomy, tubal ligation, vaginal diaphragm, intrauterine device, birth control pill, birth control implant, birth control patch, birth control depot injection, condom with spermicide, or sponge with spermicide.   |
| 2.   | Females who are breast-feeding or who have a positive pregnancy test result prior to receiving IMP.   |
| Administrative  |   |
| 3.   | Noncompliance, due to subject's failure to follow study procedures during the course of their participation in the double-blind phase 3 trial, Trial 331-10-234 (eg, subjects deemed to be noncompliant with the visit schedule, trial assessments, or treatment regimen in Trial 331-10-234). The medical monitor should be contacted if the investigator is unsure of a subject's eligibility.  |
| Target Disease  |   |
| 4.   | Subjects with a clinical presentation or history that is consistent with delirium, dementia, amnesia, or other cognitive disorders; subjects with psychotic symptoms that are better accounted for by another general medical condition(s) or direct effect of a substance (eg, medication, illicit drug use).  |
| 5.   | Subjects who have a significant risk of committing violent acts, serious self-harm, or suicide based on history (eg, suicide attempt in the past 1 year) or routine psychiatric status examination, or those who are homicidal or are considered to be a high risk to others, or who have an answer of "yes" on Questions 4 or 5 (current or over the past 1 month) on the suicidal ideation section of the "Since Last Visit" version of the C-SSRS.   |
| Medical History and Concurrent Diseases   |   |

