### 3.4.3.2 De Novo Subjects

Subjects will be excluded if they meet any of the exclusion criteria in [Table 3.4.3.2-1](#).

| Table 3.4.3.2-1 Exclusion Criteria for De Novo Subjects |   |
|--|---|
| Sex and Reproductive Status                             |   |
| 1.   | Sexually active males or females who do not agree to practice 2 different methods of birth control or remain abstinent during the trial and for 30 days after the last dose of IMP. If employing birth control, 2 of the following precautions must be used: vasectomy, tubal ligation, vaginal diaphragm, intrauterine device, birth control pill, birth control implant, birth control patch, birth control depot injection, condom with spermicide, or sponge with spermicide. |
| 2.   | Females who are breast-feeding or who have a positive pregnancy test result prior to receiving IMP.   |
| Target Disease  |   |
| 3.   | Subjects with a DSM-5 diagnosis other than schizophrenia that has been the primary focus of treatment within 3 months of screening.   |
| 4.   | Subjects with a clinical presentation or history that is consistent with delirium, dementia, amnesia, or other cognitive disorders; subjects with psychotic symptoms that are better accounted for by another general medical condition(s) or direct effect of a substance (eg, medication, illicit drug use).  |
| 5.   | Subjects who have been hospitalized > 21 days for current exacerbation of schizophrenia at the time of the baseline (Day 1) visit of the open-label treatment period.   |
| 6.   | Subjects with known intellectual disability defined as an intelligence quotient less than 70; or, either clinical evidence or known social or school history indicative of intellectual disability.   |
| 7.   | Any neurological disorder, with the exception of Tourette's Syndrome.   |
| 8.   | Subjects who have a significant risk of committing violent acts, serious self-harm, or suicide based on history (eg, suicide attempt in the past 1 year) or routine psychiatric status examination, or those who are homicidal or are considered to be a high risk to others, or who have an answer of "yes" on Questions 4 or 5 (current or over the past 1 month) on the suicidal ideation section of the "Baseline/Screening" version of the C-SSRS.                           |
| 9.   | Subjects experiencing acute depressive symptoms within the past 30 days prior to screening that, according to the investigator's judgment, require treatment with an antidepressant.  |

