8.2.6.3 Suicidality

Suicidality will be monitored during the trial (including the 1- to 4-week conversion period but excluding the 21-day follow-up period) by using the C-SSRS. A data summary will be provided separately for the open-label treatment period and for the conversion period.

Suicidality data (including suicidal ideation, suicidal behavior) will be collected at all scheduled visits and the ET visit.

Suicidal ideation has 5 types or levels, with increasing severity from “wish to be dead” to “active suicidal ideation with specific plan and intent”. The incidence of each type of suicidal ideation will be summarized for the reporting period (ie, separately for the open-label period and for the conversion period). Suicidal behavior has several types or levels ranging from “actual attempt”, “interrupted attempt”, “aborted attempt” to “completed suicide”. The incidence of each type of suicidal behavior will be summarized for the reporting period.

Additionally, the incidence of each of the following 4 categories of treatment-emergent suicidality will be summarized for the reporting period: (1) Emergence of suicidal ideation, which is defined as having an occurrence of any suicidal ideation during the reporting period while having no suicidal ideation at the baseline (relative to the reporting period); (2) Emergence of serious suicidal ideation, which is defined as having an observation of suicidal ideation severity rating of 4 or 5 during the reporting period while having no suicidal ideation at the baseline (relative to the reporting period); (3) Worsening of suicidal ideation, which is defined as having had a suicidal ideation severity rating that is more severe compared to the baseline (relative to the reporting period); and (4) Emergence of suicidal behavior, which is defined as reporting of any suicidal behavior during the reporting period while there was no suicidal behavior at the baseline (relative to the reporting period). Specifically, for each category of treatment-emergent suicidality as defined above, the number and percentage of subjects having experienced the event of interest during the reporting period will be tabulated.

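### Protocol Section 3.7.3.5.7 and the exclusion tables it cites set different suicidality entry rules, so a subject with lower-level active ideation or non-attempt behavior can be excluded by one and eligible under the other

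*Protocol*

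**What the plan says.** Three places in the protocol set a suicidality entry rule.

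- **Section 3.7.3.5.7** names "Any subject with active suicidal ideation within the last 30 days, suicidal behaviors within the last year". It adds a third ground, that anyone who in the "clinical judgment of the investigator presents a serious risk of suicide should be excluded from the trial". It gives no severity level for active ideation. It then refers to Table 3.4.3.1-1 for rollover subjects and Table 3.4.3.2-1 for de novo subjects.
- **Table 3.4.3.1-1, criterion 5 (rollover)** uses the Since Last Visit version of the C-SSRS and excludes on ideation for a positive answer "on Questions 4 or 5 (current or over the past 1 month) on the suicidal ideation section of the" form.
- **Table 3.4.3.2-1, criterion 8 (de novo)** sets the same threshold, a yes "on Questions 4 or 5 (current or over the past 1 month) on the suicidal ideation section", but on the Baseline/Screening version.

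Both criteria also contain a separate ground, joined by *or*: significant risk of violence, self-harm or suicide, "based on history (eg, suicide attempt in the past 1 year) or routine psychiatric status examination". Each table also has a general exclusion at the investigator's opinion (criterion 14 for rollover subjects, criterion 25 for de novo subjects).

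SAP Section 8.2.6.3 describes the scale. "Suicidal ideation has 5 types or levels, with increasing severity from" a wish to be dead up to active ideation with a specific plan and intent. The SAP defines emergent serious ideation by "having an observation of suicidal ideation severity rating of 4 or 5 during the reporting period", in a subject with none at baseline. "Suicidal behavior has several types or levels ranging from" actual, interrupted and aborted attempts to completed suicide.

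**The concern.** Section 3.7.3.5.7 sends the reader to the tables for the same rule, but the tables state a different one. A site working from the assessment section and a site working from the eligibility tables could reach opposite decisions on the same adolescent.

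Two things are at stake. The first is safety at entry: this is a suicidality criterion for adolescents, and it should not depend on which page a site reads. The second is reporting. Protocol Section 3.13 gives enrolment against the eligibility criteria as an example of a significant deviation, and SAP Section 6.3 summarizes deviations in entry criteria. With two rules in force, whether a given subject is a deviation depends on which text the person classifying it uses.

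**Working it through.** No arithmetic applies, and the plan states no figure on this point. The check sets the texts side by side and then runs cases through them.

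| Element | Section 3.7.3.5.7 | Both tables (criterion 5; criterion 8) | Agree? |
|---|---|---|---|
| Ideation threshold | Active ideation, no level stated | Yes on Question 4 or 5 | No |
| Ideation look-back | 30 days | Current or past month | Yes |
| Behavior | Suicidal behaviors, without limit of type | A suicide attempt, as an example of history showing significant risk | No |
| Behavior look-back | One year | One year | Yes |
| Investigator's judgment | Serious risk of suicide | Significant risk from history or examination, plus the general opinion criterion | Similar |

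**Step 1: ideation.** The SAP gives five levels of increasing severity, so Questions 4 and 5 are the top two. Section 3.7.3.5.7 does not limit itself to those two.

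**Step 2: behavior.** The SAP lists interrupted and aborted attempts as types of suicidal behavior, separate from an actual attempt. Section 3.7.3.5.7 covers all types. The tables name an attempt only, and only as an illustration; they do not say whether an interrupted or aborted attempt counts as one.

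**Step 3: cases.**

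| Subject | Section 3.7.3.5.7 | Tables |
|---|---|---|
| Yes on Question 4 or 5 in the past month | Excluded | Excluded |
| Active ideation below Question 4 in the past month, judged at significant risk | Excluded | Excluded |
| Active ideation below Question 4 in the past month, no behavior in the past year, not judged at significant risk or otherwise unsuitable | Excluded | Eligible |
| Interrupted or aborted attempt in the past year, no recent ideation, not judged at significant risk or otherwise unsuitable | Excluded | Eligible, unless the site reads it as a suicide attempt |

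The texts diverge in the third and fourth rows. The divergence is the same for rollover and de novo subjects, because the two tables use the same thresholds.

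**Step 4: precedence.** Section 3.4.3 says subjects meeting any criterion in the tables will be excluded. Section 3.7.3.5.7 says subjects meeting its own description should be excluded. Neither says that it overrides the other.

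**The case against.** The strongest reply is that there is only one operative rule. Section 3.4.3 is the eligibility section and its tables are the criteria. Section 3.7.3.5.7 describes an assessment, uses the softer *should*, and points to the tables by number. On that reading it is a loose paraphrase, and a site that follows the reference will apply the tables.

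This is a fair reading, and some sites may adopt it. It is why different enrolment across sites is possible rather than certain. A reader might infer that sites will enrol different adolescents; the documents do not show that. But the protocol nowhere says the tables prevail, and a sentence that excludes a subject is not a paraphrase of a criterion that admits the same subject.

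The second reply is that investigator judgment narrows the gap, and it does. A reader might infer that the tables exclude on Questions 4 or 5 alone, so that every subject with lower-level active ideation falls into the gap. That is not supported: the significant-risk ground and the general opinion criterion will remove some of them. What remains is the group the investigator considers neither at significant risk nor otherwise unsuitable.

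The third reply is that the C-SSRS form is not in the supplied text, so which levels below 4 count as active cannot be confirmed. That stands as a limit. The SAP's description of the top level, which adds a specific plan and intent to active ideation, suggests that active ideation also exists without them, but this is not proof. The difference on behavior does not depend on this point.

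**Conclusion.** The point holds as a contradiction in current text. Section 3.7.3.5.7 and the two tables differ on the ideation threshold and on which behavior excludes. The affected group is subjects with active ideation below Question 4, or suicidal behavior other than an attempt, who are not judged to be at significant risk. Its size is unknown, because neither document gives a frequency. It is worth correcting because the rule concerns safety at entry and the correction is cheap.

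The ideation part assumes that at least one level below Question 4 counts as active. The behavior part assumes that an interrupted or aborted attempt is not read as a suicide attempt under the tables.

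Three further inferences are tempting and not supported:

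- **Conflicting look-back periods between the texts.** They agree: 30 days against one month, and one year against one year.
- **A compromised baseline for emergent suicidality.** SAP Section 7.1 defines baseline without reference to the entry rule. The rule applied can shift the case mix: under SAP Section 8.2.6.3 a subject with ideation at baseline can count as worsening but not as emergent. It does not change the definitions, and the trial is single-arm with no inferential analysis planned.
- **A proven mismatch between the rollover form and its question.** Criterion 5 asks about the past month on a form whose name suggests it covers only the interval since the previous visit. That is an assumption from the name. The form and the parent trial's visit schedule are not supplied, so it is a secondary point to confirm.

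**What to change.** Reconcile Section 3.7.3.5.7 with criterion 5 of Table 3.4.3.1-1 and criterion 8 of Table 3.4.3.2-1, so that all three state one ideation threshold and one behavior criterion. The behavior criterion should say which types count. Alternatively, add a sentence saying which text governs. The choice of rule is the sponsor's clinical decision, and none is proposed here.

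As a secondary check, confirm that the Since Last Visit form can answer the past-month question for rollover subjects, and if it cannot, reconcile the form and the question.

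The cost is protocol wording in three places, with no change to assessments, sample size or analyses. If enrolment has already ended, which the documents do not establish, it is still worth recording which text is used to classify eligibility deviations, so that the SAP Section 6.3 summary rests on one rule.
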